7.5 SECONDARY ENDPOINTS

7.5.1 Key secondary endpoints

This section is not applicable as no key secondary endpoint has been specified in the protocol.

7.5.2 (Other) Secondary endpoints

Section 7.3.2 of the CTP:

The secondary endpoints (refer to [Section 5.2.2](#)) will be calculated according to the BI SOP 'Standards and processes for analyses performed within Clinical Pharmacokinetics/ Pharmacodynamics' (BI-KMED-TMCP-MAN-0014 ([5](#))) and will be assessed statistically using the same methods as described for the primary endpoints.

Safety and tolerability endpoints

Refer to [Section 7.8](#) for a description of the analysis of safety and tolerability.

7.7 EXTENT OF EXPOSURE

Descriptive statistics are planned for this section of the report based on the TS. The date and time of each drug administration will be listed for each subject.

7.8 SAFETY ANALYSIS

All safety analyses will be performed on the TS.

The safety data for treated subjects who failed to complete the study (dropouts or withdrawals) will be reported as far as their data are available. All withdrawals will be documented and the reason for withdrawal recorded.

7.8.1 Adverse Events

Unless otherwise specified, the analyses of AEs will be descriptive in nature. All analyses of AEs will be based on the number of subjects with AEs and NOT on the number of AEs. BI standards as presented in “Analysis and Presentation of Adverse Event Data from Clinical Trials – Display Template” [BI-KMED-BDS-HTG-0041] (9) and [BI-KMED-BDS-HTG-0066] (10) will be applied.

The analysis of AEs will be based on the concept of treatment emergent AEs. That means that all AEs will be assigned to ‘screening’ or ‘on-treatment’ phases as defined in [Section 6.1](#). AEs will be analysed based on actual treatments, as defined in [Table 6.1: 1](#).

According to the clinical study protocol, adverse events of special interest (AESI) will be analysed:

Section 5.2.7.1.4 of the CTP: *The following are considered as AESIs:*

- **Hepatic injury**
A hepatic injury is defined by the following alterations of hepatic laboratory parameters:
 - o *An elevation of AST (aspartate transaminase) and/or ALT (alanine transaminase) ≥ 3 -fold ULN combined with an elevation of total bilirubin ≥ 2 -fold ULN measured in the same blood sample, or*
 - o *Aminotransferase (ALT, and/or AST) elevations ≥ 10 fold ULN*

According to ICH E3 (11), in addition to deaths and serious adverse events, ‘other significant’ AEs need to be listed in the clinical trial report. These will be any non-serious adverse event that led to an action taken with study drug (e.g. discontinuation or dose reduced or interrupted).

An overall summary of adverse events will be presented.

The frequency of subjects with AEs will be summarised by treatment, primary system organ class (SOC) and preferred term (PT). Separate tables will be provided for subjects with serious AEs, for subjects with drug-related AEs, for subjects with drug-related serious adverse events and for subjects with AESIs. In addition, the frequency of subjects with AEs will be summarised by treatment, worst intensity, primary SOC and PT.

The SOCs and PTs will be sorted by frequency (within SOC). The MedDRA version number will be displayed as a footnote in the respective output.

In addition, frequencies of subjects with non-serious AEs that had an incidence of $> 5\%$ for at least one treatment will be summarised by treatment, primary SOC and PT.

For disclosure of adverse events on EudraCT, additional information not included in a standard AE analysis will be performed. The following three entries will be created:

- Adverse Events per arm for disclosure on EudraCT
- Non-serious Adverse Events for disclosure on EudraCT
- Serious Adverse Events for disclosure on EudraCT

7.8.2 Laboratory data

The analyses of laboratory data will be descriptive in nature and will be based on BI standards [BI-KMED-BDS-HTG-0042] ([12](#)).

Laboratory data will be analysed qualitatively via comparison of laboratory data to their reference ranges. Values outside the reference range as well as values defined as possibly clinically significant will be flagged in the data listings.

Clinically relevant findings in laboratory data will be reported as baseline conditions (at screening) or as AEs (during the trial) if judged clinically relevant by the investigator, and will be analysed as such.

It is the investigator's responsibility to decide whether a lab value is clinically significantly abnormal or not (at the RPM at the latest).

Descriptive statistics of laboratory data including change from baseline will be calculated by planned time point based on the worst value of the subject at that planned time point (or assigned to that planned time point).

7.8.3 Vital signs

Descriptive statistics over time including change from baseline will be performed for vital signs (blood pressure, pulse rate and body temperature). In the listing the difference from baseline will also be displayed.

For vital signs, descriptive statistics will be calculated by planned time point based on the last value of the subject at that planned time point (or assigned to that planned time point).

Clinically relevant findings in vital signs will be reported as AEs.

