#### Cardiovascular system

BI 1595043 was tested for blocking hERG-mediated potassium current in HEK293 cells ( $\underline{n00270147}$ ). BI 1595043 inhibited the current with the IC50 of 157.88  $\mu$ M or 233-times the estimated human therapeutic C_{max}. Effect of BI 1595043 on cardiovascular function was assessed in conscious male telemetry-instrumented Beagle dogs at oral doses of 3, 10 or 200 mg/kg ( $\underline{n00271655}$ ). At doses of 3 and 10 mg/kg, no BI 1595043-related abnormalities were observed. At 200 mg/kg of BI 1595043, decrease in blood pressure with accompanying increase in heart rate were observed.

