## 1.4.3.6 Risk minimization (safety precautions and stopping rules)

The following risk minimization measures, including safety precautions and stopping rules, will be implemented in this study:

- Careful selection of the study dose, as described in Section 4.1.2.
- If dosing of several subjects is scheduled on a same day, subjects will be dosed at least 5 min apart.
- Application of the second single dose of BI 1595043 to each subject, only if the first single dose of BI 1595043 is safe, shows acceptable tolerability, and no stopping criterion is met (see Sections 3.3.4.1 and 3.3.4.3). At least 8 days will be maintained between the two drug administrations to each subject.
- A monitoring of safety laboratory with specific focus on plasma glucose levels and liver enzymes (see Flow Chart).
- Safety monitoring (including e.g. vital signs, 12-lead ECGs and adverse events) with a special focus on blood pressure and heart rate measurements.
- Ophthalmological examination at Screening and EoTrial Visit (see Section 5.2.3).

Page 30 of 75

Proprietary confidential information © 2021 Boehringer Ingelheim International GmbH or one or more of its affiliated companies

- Hospitalization of subjects at the trial site for at least 48 hours after study drug administration at each dose level. Based on the longest gMean terminal t_{1/2} in dose group 5 of up to 29.3 h (based on preliminary PK data) for BI 1595043 in this study, this is expected to cover the period of highest risk/ peak effect. During in house-confinement, subjects will be under medical observation and thoroughly monitored for both expected and unexpected adverse events.
- Exclusion of acetaminophen (paracetamol) as concomitant medication.
- Due to observed teratogenicity in rat, women will not be enrolled in this study.

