#### 6.2.3 Follow-up period and trial completion

For AE assessment, laboratory tests, recording of ECG and vital signs, and physical examination during the follow-up period, see Sections 5.2.2 to 5.2.5. Subjects who discontinue treatment before the end of the planned treatment period should undergo the EoTrial Visit.

All abnormal values (including laboratory parameters) that are assessed as clinically relevant by the investigator will be monitored using the appropriate tests until a return to a medically acceptable level is achieved. (S)AEs persisting after a subject's EoTrial Visit must be followed until they have resolved, have been sufficiently characterised, or no further information can be obtained.

34388550-04 Trial Protocol Page 56 of 75

Proprietary confidential information © 2021 Boehringer Ingelheim International GmbH or one or more of its affiliated companies

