6.7 BASELINE, TIME WINDOWS AND CALCULATED VISITS

The baseline value is defined as the last measurement before study drug administration in each treatment period. For laboratory data, baseline for both periods is the last measurement before study drug administration in the first period (-72:00).

Section 6.1 of the CTP: Study measurements and assessments scheduled to occur 'before' trial medication administration on Day 1 are to be performed and completed within a 3 h-period prior to the trial drug administration.

The acceptable deviation from the scheduled time for vital signs, ECG, and laboratory tests will be ± 15 min for the first 4 h after trial drug administration and ± 30 min thereafter. Starting from 48 h post-dose a deviation from the scheduled time for vital signs, ECG and laboratory tests of ± 120 min is acceptable.

Adherence to time windows will be checked via the consistency check listings at the RPM.

Unscheduled measurements of laboratory data and vital signs data will be assumed to be repeat measurements of the most recent scheduled measurement (e.g. for follow-up or confirmation of a particular value). Therefore, unscheduled measurements will be assigned to the planned time point of the previous scheduled measurement.

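### SAP 7.8.3 summarises vital signs by the last value at each time point, so a repeat can displace an abnormal post-dose BP or pulse reading in the descriptive table; a summary of post-dose extremes should be added

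*SAP*

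**What the plan says.** Two SAP rules act together. SAP 6.7 states: "Unscheduled measurements of laboratory data and vital signs data will be assumed to be repeat measurements of the most recent scheduled measurement". It concludes that "unscheduled measurements will be assigned to the planned time point of the previous scheduled measurement". No limit is set on how late such a reading may be. SAP 7.8.3 then calculates the vital-sign statistics by planned time point "based on the last value of the subject at that planned time point", and a parenthesis extends this to values assigned to that time point. SAP section 7 gives the statistics as N, mean, SD, minimum, median and maximum; 7.8.3 adds change from baseline.

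For laboratory data the assignment rule is the same but the choice of value differs. SAP 7.8.2 works "based on the worst value of the subject at that planned time point".

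On re-measurement, protocol 6.2.3 says of "All abnormal values (including laboratory parameters) that are assessed as clinically relevant by the investigator" that they "will be monitored using the appropriate tests until a return to a medically acceptable level is achieved".

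Protocol 1.4.3.6 plans safety monitoring "with a special focus on blood pressure and heart rate measurements". Part of the background is the dog telemetry study, where at 200 mg/kg a "decrease in blood pressure with accompanying increase in heart rate were observed" (protocol 1.2.1.2).

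**The concern.** A vital-sign reading may be repeated because the scheduled one looked abnormal. If it has normalised by the repeat, the last-value rule puts the normal reading into the table under the scheduled time label and leaves the abnormal one out. A short-lived fall in BP or rise in pulse is the pattern the protocol says it is watching for, and the table of vital signs over time is where a reader would look for it by treatment.

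The time label can also mislead. SAP 6.7 accepts scheduled readings only within 15 minutes up to 4 h, 30 minutes after that and 120 minutes from 48 h, yet an unscheduled reading taken hours later can stand as the value for the earlier time point.

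At stake is how well the descriptive safety summary shows transient haemodynamic excursions under fed and fasted dosing. No inferential result depends on it.

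**Working it through.** The plan attaches no figure to this rule, so there is nothing to reproduce. The check is a reading of the rules in sequence, followed by an illustration of size.

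**Step 1: which value enters the table.** Take an abnormal BP at the scheduled 1 h measurement, repeated before the 2 h measurement.
- SAP 6.7 assigns the repeat to 1 h.
- SAP 7.8.3 takes the last value at 1 h, which is the repeat.
- The on-time reading then contributes to none of the statistics for 1 h.

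**Step 2: how late the displacing value can be.** The protocol Flow Chart schedules post-dose BP and pulse at 1, 2, 4, 8, 12, 24 and 48 h. The gaps between them are 1, 2, 4, 4, 12 and 24 h. A reading can therefore be carried back by just under the length of the gap it falls in: just under 12 h for the 12 h label and just under 24 h for the 24 h label.

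**Step 3: where the displaced reading still appears.**
- Listings: SAP section 7 lists all individual values, and SAP 7.8.3 adds the difference from baseline for vital signs.
- AE tables: SAP 7.8.3 and protocol 5.2.7.1.1 have vital-sign findings judged clinically relevant reported as AEs; SAP 7.8.1 tabulates AEs by treatment, SOC, preferred term and worst intensity.
- Not covered by the AE route: a reading that was repeated but not judged clinically relevant. It survives only in the listing. SAP 7.8.2 flags out-of-range laboratory values in listings; SAP 7.8.3 specifies no such flag for vital signs.

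**Step 4: size (illustration).** The inputs are N = 14 (protocol 7.7) and assumed readings. The shift in the mean change at a time point is

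shift = sum over repeated subjects of (last value - scheduled value) / N.

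- One subject, -30 to -5 mmHg: (-5 + 30)/14 = 25/14 = 1.8 mmHg.
- Two such subjects: 50/14 = 3.6 mmHg.
- Full recovery (last value 0) from assumed falls of 20 to 40 mmHg in k subjects gives k x fall/14:

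| k | 20 mmHg | 30 mmHg | 40 mmHg |
|---|---|---|---|
| 1 | 1.4 | 2.1 | 2.9 |
| 2 | 2.9 | 4.3 | 5.7 |
| 3 | 4.3 | 6.4 | 8.6 |

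The minimum and SD can change more visibly than the mean. Suppose two subjects are at -30 and recover to -2, and the other twelve are at 0:
- scheduled values: mean -60/14 = -4.3, SD 10.9, minimum -30;
- last values: mean -4/14 = -0.3, SD 0.7, minimum -2.

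With no repeats the two versions are identical.

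**The case against.** The case for leaving the rule alone has real force.

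- **The reading is not lost.** A reader might infer that an abnormal value disappears from the report. It does not: it stays in the listing with its difference from baseline. The values that protocol 6.2.3 requires to be followed are those judged clinically relevant, which are the ones that also become AEs. This stands, and it limits the point to one descriptive table.
- **Repeats need not end normal.** A reader might infer that the last reading is always the recovered one, so that the rule always pulls towards normal. SAP 6.7 names confirmation of a value as well as follow-up. A repeat may correct a false reading, or may be worse than the first. The documents do not say that repeats are taken mainly after abnormal readings. Protocol 6.2.3 is a general sentence under follow-up and trial completion; it does not prescribe serial BP readings on the dosing day. This stands too, so the direction is conditional.
- **Last for vital signs and worst for laboratory data is not a contradiction.** BP and pulse can be abnormal in either direction, so worst would need a definition for each parameter. The SAP gives no reason for the difference, but it is a difference of convention.
- **The stakes are modest.** The dog finding was at 200 mg/kg, with none at 3 or 10 mg/kg. Vital signs showed no relevant findings in the completed groups up to 90 mg (protocol 1.2.5.1). A fall that persists is still seen at the next scheduled reading.

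What remains is that the AE route depends on investigator judgement and a listing is not a summary by treatment. For ECGs, protocol 5.2.5 says repeats for quality reasons are used for analysis. Nothing comparable confines the vital-sign rule to technically faulty readings.

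**Conclusion.** The point holds as a limited one. As written, the SAP lets a repeat displace the on-time post-dose reading in the by-time-point vital-sign table. When the repeat has recovered, the excursion drops out of the mean, minimum, maximum and change from baseline for that time point. The consequence is greatest for excursions not judged clinically relevant, because those have no AE entry.

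The size cannot be stated from the documents. The 1.8 mmHg for one subject rests on 14 subjects at the time point, an assumed -30 mmHg reading, and an assumed repeat of -5 mmHg before the next scheduled measurement.

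A reader might also infer that the rule hides a difference between fed and fasted dosing. That would need displaced readings to be more frequent or larger under one treatment. Nothing in the documents shows this, and protocol 4.1.2 expects food to affect exposure minimally. The primary and secondary PK analyses do not use these data. The change is worth making because it is cheap and concerns the parameters the protocol singles out for safety monitoring.

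**What to change.** **Main change.** In SAP 7.8.3, add a summary for each treatment (fed and fasted) of each subject's lowest post-dose systolic BP, lowest post-dose diastolic BP and highest post-dose pulse rate. Include change from baseline and all unscheduled readings, and state the post-dose interval covered. An excursion then stays visible whichever value the time-point table uses.

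**Preferred addition.** Base the by-time-point statistics on the scheduled measurement, and use a repeat only when the first reading is documented as technically invalid. This is partly a choice of convention, so it ranks second. It also keeps the time labels true to the scheduled times.

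**Cost.** One extra table and a few lines of SAP text; no new data and no effect on the PK analysis. The downside is that an unconfirmed false reading may remain in the summary unless it is documented as invalid. Extremes also depend on how many readings a subject has, so the table should be read beside the listing.

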7.8.4 ECG

ECG recordings will be checked by the investigator for pathological results. Clinically relevant abnormal findings for ECG will be listed under 'Relevant Medical History / Baseline Conditions' (when they occurred during screening) or will be reported as AEs (when they occurred during treatment), and will be analysed as such.

No separate ECG listing will be provided.

7.8.5 Others

Physical examination

Physical examination findings will be reported as relevant medical history/baseline condition (i.e., a condition already existent before intake of study drug) or as AE and will be summarised as such.

No separate listing or analysis of physical examination findings will be prepared.

8. TIMEPOINT OF RELEASE OF TREATMENT INFORMATION

The treatment information will be loaded into the trial database after completion of enrolment, i.e. the randomization has been completed.

11. HISTORY TABLE

Table 11: 1 History table

Version	Date (DD-MMM- YY)	Author	Sections changed	Brief description of change
1	30-AUG-21		None	This is the final TSAP
